4.11 Patient Replacement

If a patient is enrolled in the study but comes off study prior to the first dose of treatment, the patient may be replaced.

If a subject in the safety run-in portion of the trial goes off treatment before completing the DLT observation period of safety run-in for reasons other than DLT, then a patient will need to be added to the safety run-in.

5.0 STUDY PROCEDURES AND SCHEDULE OF EVENTS**5.1 COMBINATION TREATMENT GUADECITABINE + PEMBROLIZUMAB**

Time Period	Screening		On Treatment ¹⁵			Off Treatment	
	≤28 days prior to registration	≤14 days prior to registration	Cycle 1 ¹⁴	Cycle 2	Subsequent cycles	≥ 6 months of treatment ¹⁷	30 days post last dose ¹²
Required Assessments							
Informed Consent	X						
Medical history ¹	X						
Physical exam ²		X	D1 ²	D1 ²	D1 ²		X
CBC ³		X	D1 ³	D1 ³	D		X
CMP ³		X	D1 ³	D1 ³	D		X
CA 125 ³	X		D1 ³	D1 ³	D		X
Mg, Phos, LDH		X					
PT/INR & aPTT		X					
Thyroid Function and Uric acid ¹¹		X			D1 ¹¹		
Pregnancy test	X ⁸		D1 ⁸	D1 ⁸	D1 ⁸		
Adverse events ¹⁶		X	D1	D1	D1		X
Con Meds ¹⁶		X	D1	D1	D1		X
CXR or CT of chest ⁴	X				X		X ¹³
CT or MRI of abdomen & pelvis ⁴	X				X		X ¹³
Pembrolizumab ¹⁵			D5	D5	D5		
Guadecitabine ¹⁵			D1-4	D1-4	D1-4		
Archival tumor tissue ⁵			X				
Blood for DNA analysis ⁶			C1D1	C2D8		X ¹⁷	
Blood for cytokine response ⁷			C1D1	C2D1	C3D1	X ¹⁷	X
Blood for PBMC analysis ⁹			X	X		X ¹⁷	X
Tumor biopsy ¹⁰			X	X		X ¹⁷	
Survival status							X
Subsequent therapy							X

1. Includes diagnosis and staging [pathology report and Tumor Node Metastasis (TNM) staging should be collected].

2. Physical exam includes vital signs [blood pressure, weight, height (screening only)] and ECOG performance status. Physical exam will be conducted on Day 1 (+/-4 days) of each cycle and at the safety follow-up visit, which occurs 30 days post last dose.

3. Labs to be done within ≤4 days of D1. Cycle 1 Day 1 CBC and CMP do not need to be repeated if screening labs

NU Study Number: NU 16G03

Merck Study Number: 3475-244

were done ≤ 4 days prior to starting treatment. CA-125 is to be drawn at screening and Day 1 of each cycle. Exceptions would be if CA-125 was drawn within 14 days from the screening visit or within 14 days of visits where doses have been delayed. In these cases, CA-125 will not need to be re-drawn. CBC = Complete Blood Cell Count with diff. CMP = Na, K, Cl, creatinine, BUN; liver function tests (LFTs) to include AST, ALT, total bilirubin, alkaline phosphatase.

4. Tumor response assessment will consist of evaluation by CXR or CT scans of chest and MRI or CT of abdomen and pelvis. Screening radiologic imaging should be done ≤ 28 days prior to registration. During treatment, radiologic imaging should be done prior to Cycle 3 and cycle 5 and then prior to every third cycle thereafter (e.g. prior to cycles 8, 11, 14, etc.). *Radiologic imaging can be obtained ≤ 7 days prior to day 1 of the cycle.* The imaging modality selected for each subject should remain the same throughout the study. *Responses of PD, PR, or CR should be confirmed within 4-6 weeks, at the discretion of the treating physician.* (Refer to section 6.0 for more details).
5. Formalin fixed paraffin-embedded tissue will be requested from an archived tumor specimen from all subjects (required to submit, if available). The archived tumor tissue specimens may be from surgery or from a diagnostic biopsy of primary or metastatic tumor specimen, and may be procured up to 3 months from registration. Unavailability of archived tissue will not render subject ineligible for study. See Section 9 and laboratory manual for additional details.
6. Blood for DNA analysis will be collected on Cycle 1 Day 1 [≤ 7 days] and Cycle 2 Day 8 [+2 days]. See Section 9 and laboratory manual for additional details.
7. Blood for cytokine response will be collected at pre-treatment on Cycle 1 Day 1 (≤ 4 days), Cycle 2 Day 1 (≤ 4 days), Cycle 3 Day 1 (≤ 4 days), and at the safety follow up visit. See Section 9 and laboratory manual for additional details.
8. Pregnancy test required only for females of child-bearing potential ≤ 7 days prior to registration. Also, pregnancy test will be done on D1 (≤ 4 days) of each cycle for females of child bearing potential.
9. Blood for PBMC analysis will be collected at pre-treatment Cycle 1 Day 1 (≤ 4 days), Cycle 1 Day 5, pre-treatment on Cycle 2 Day 1 (≤ 4 days), Cycle 2 Day 5, and at the safety follow up visit. See Section 9 and laboratory manual for additional details.
10. Tumor biopsies [guided by CT, ultrasound, or physical exam, according to the discretion of the treating physician], and/or paracentesis, and/or thoracentesis will occur after registration and prior to the start of treatment [(Cycle 1 Day 1 (≤ 7 days)) and Cycle 2 Day 8 (+2 days) if clinically feasible for the subject. See Section 9 and laboratory manual for additional details.
11. Thyroid Function (TSH with reflex testing only if abnormal findings) and uric acid to be performed at screening and D1 (≤ 4 days) of every odd cycle beginning with Cycle 3.
12. Safety follow-up visit will occur 30 days (± 7 days) after the last dose of study therapy or before the initiation of a new anti-cancer treatment, whichever is first. Please refer to section 7 for tracking and reporting of AEs/SAEs.
13. Subjects who discontinue trial treatment for a reason other than disease progression should be assessed every 9 weeks (± 7 days) by radiologic imaging to monitor disease status until the start of new anti-neoplastic therapy, disease progression, death or end of the study. Information regarding post-study anti-neoplastic treatment will be collected if new treatment is initiated. Once a subject experiences confirmed disease progression or starts a new anti-cancer therapy, the subject should be contacted *by telephone, email, or a clinic visit every 3 months for the first 2 years and then every 6 months thereafter to assess for survival status until death, withdrawal of consent, or the end of the study, whichever occurs first.*
14. Cycle 1 day 1 should be started within (+) 14 days following registration.
15. Patients should begin treatment within 14 days of registration. While on treatment, day 1 of each cycle may be delayed up to +28 days from the target date for scheduling purposes and holidays. *NOTE: Due to the dosing of guadecitabine on days 1-4 followed by pembrolizumab on day 5, it is recommended that day 1 of each guadecitabine cycle should occur on a Monday.*
Note: Guadecitabine priming can be discontinued and the patient can continue on pembrolizumab monotherapy after 6 months (8 cycles), at the discretion of the treating physician, if the patient has stable disease or response. If this is done, please follow the pembrolizumab monotherapy dosing table (section 5.2).

NU Study Number: NU 16G03

Merck Study Number: 3475-244

16. ConMeds and AE assessment are to be completed from on D1 of each cycle (+/-4 days). ConMeds will also be recorded up to 30 days after the last dose of trial treatment. Concomitant medications administered beyond 30 days after the last dose of trial treatment for management of study-related toxicity should be recorded for SAEs and Events of Clinical Interest (ECIs).
AE assessments will also be done 30 days after the last dose of trial treatment OR until start of next anti-cancer treatment (whichever is first).
SAEs will be recorded for 90 days after the last dose of trial treatment.
17. OPTIONAL tests for patients who have been on treatment for ≥ 6 months. Samples can be collected at any time from ≥ 6 months and before the safety follow-up visit.
Tumor biopsies or paracentesis or thoracentesis may be done. This will be guided by CT, ultrasound, or physical exam, according to the discretion of the treating physician. *All samples will be for research purpose.*
See Section 9 and laboratory manual for additional details.

NU Study Number: NU 16G03
Merck Study Number: 3475-244

5.2 PEMBROLIZUMAB MONOTHERAPY

Pembrolizumab monotherapy is indicated for:

- Patients who discontinue guadecitabine after 2 cycles due to toxicity and who continue on pembrolizumab monotherapy.
- Patients who discontinue guadecitabine after 8 cycles due to SD or PR or CR and who continue on pembrolizumab.

In the above cases, D5 will become D1. D1 assessments will now be performed in respect to pembrolizumab D1 dosing instead of guadecitabine D1 dosing.

	On Treatment	Off Treatment	
Time Period	D1 of each cycle (-/+ 2 days)	30 days post last dose¹¹	Long term Follow-up
Required Assessments			
Physical exam ¹	D1	X	
CBC ²	D1 ²	X	
CMP ²	D1 ²	X	
CA 125 ²	D1 ²	X	
Thyroid Function and Uric acid ³	D1		
Pregnancy test ⁴	D1		
Adverse events ⁵	D1	X	X
Con Meds ⁵	D1	X	X
CXR or CT of chest ⁶	X ⁶		X ¹²
CT or MRI of abdomen & pelvis ⁶	X ⁶		X ¹²
Pembrolizumab monotherapy ⁷	D1		
Archival tumor tissue ⁸	X		
Blood for cytokine response ⁹	C3D1	X	
Blood for PBMC analysis ¹⁰	X	X	
Survival status			X ¹²
Subsequent therapy			X

¹ Physical exam includes vital signs [blood pressure, weight, height (screening only)] and ECOG performance status. Physical exam will be conducted on Day 1 (+/-4 days) of each cycle and at the safety follow-up visit, which occurs 30 days post last dose.

² Labs to be done within ≤ 4 days of D1. CA-125 is to be drawn at Day 1 of each cycle. Exceptions would be if CA-125 was drawn within 14 days of visits where doses have been delayed. In these cases, CA-125 will not need to be re-drawn. CBC = Complete Blood Cell Count with diff. CMP = Na, K, Cl, creatinine, BUN; liver function tests (LFTs) to include AST, ALT, total bilirubin, alkaline phosphatase.

³ Thyroid Function (TSH with reflex testing only if abnormal findings) and uric acid to be performed at D1 (≤ 4 days) of every odd cycle beginning with Cycle 3.

NU Study Number: NU 16G03

Merck Study Number: 3475-244

⁴ Pregnancy test will be done on D1 (≤ 4 days) of each cycle for females of child bearing potential.

⁵ ConMeds and AE assessment are to be completed from on D1 of each cycle (+/-4 days). ConMeds will also be recorded up to 30 days after the last dose of trial treatment. Concomitant medications administered beyond 30 days after the last dose of trial treatment for management of study-related toxicity should be recorded for SAEs and Events of Clinical Interest (ECIs).

AE assessments will also be done 30 days after the last dose of trial treatment OR until start of next anti-cancer treatment (whichever is first).

SAEs will be recorded for 90 days after the last dose of trial treatment.

⁶ Tumor response assessment will consist of evaluation by CXR or CT scans of chest and MRI or CT of abdomen and pelvis. During treatment, radiologic imaging should be done prior to Cycle 3 and Cycle 5 and then prior to every third cycle thereafter (e.g. prior to cycles 8, 11, 14, etc.). *Radiologic imaging can be obtained ≤ 7 days prior to day 1 of the cycle.* The imaging modality selected for each subject should remain the same throughout the study. *Responses of PD, PR, or CR should be confirmed within 4-6 weeks, at the discretion of the treating physician.* (Refer to section 6.0 for more details).

⁷ Pembrolizumab 200 mg will be administered as a 30-minute intravenous (IV) infusion every 3 weeks.

Pembrolizumab monotherapy dosing will be on Fridays (-/+ 2 days) and D1 assessments will now be performed in respect to pembrolizumab D1 dosing instead of guadecitabine D1 dosing.

⁸ Formalin fixed paraffin-embedded tissue will be requested from an archived tumor specimen from all subjects (required to submit, if available). The archived tumor tissue specimens may be from surgery or from a diagnostic biopsy of primary or metastatic tumor specimen, and may be procured up to 3 months from registration. Unavailability of archived tissue will not render subject ineligible for study. See Section 9 and laboratory manual for additional details. (Please contact Principal Investigator or Lead site study- coordinator for any questions or concerns)

⁹ Blood for cytokine response will be collected at pre-treatment on Cycle 3 Day 1(≤ 4 days), and at the safety follow up visit. See Section 9 and laboratory manual for additional details.

¹⁰Blood for PBMC analysis will be collected at pre-treatment Cycle 1 Day 1(≤ 4 days), Cycle 1 Day 5, pre- treatment on Cycle 2 Day 1(≤ 4 days), Cycle 2 Day 5, and at the safety follow up visit. See Section 9 and laboratory manual for additional details.

¹¹Safety follow-up visit will occur 30 days (± 7 days) after the last dose of study therapy or before the initiation of a new anti-cancer treatment, whichever is first. Please refer to section 7 for tracking and reporting of AEs/SAEs.

¹²Subjects who discontinue trial treatment for a reason other than disease progression should be assessed every 9 weeks (± 7 days) by radiologic imaging to monitor disease status until the start of new anti- neoplastic therapy, disease progression, death or end of the study. Once a subject experiences confirmed disease progression or starts a new anti-cancer therapy, the subject should be contacted by telephone, email, or a clinic visit every 3 months for the first 2 years and then every 6 months thereafter to assess for survival status until death, withdrawal of consent, or the end of the study, whichever occurs first.

6.0 ENDPOINT ASSESSMENT

6.1 Definitions

Response assessments will be made both using the Immune Related Response Criteria (irRC), and using RECIST v1.1 (See table below), allowing additional comparisons among these criteria for disease response assessment. Measurable and non-measurable lesions will be followed by both RECIST v1.1 & irRC. Disease progression will be determined using RECIST 1.1 criteria (The Response Evaluation Criteria in Solid Tumors (RECIST) 1.1. Eur J Can, 2009;45:p.228-247). Refer to the RECIST1.1 publication for complete details on these criteria. At the first disease assessment, treatment can be continued, even in the presence of radiographic or clinical progression, if in the opinion of the treating physician, the patient is stable or benefitting clinically. In that circumstance, a short-term follow up scan should be obtained in 4-6 weeks.

NU Study Number: NU 16G03
Merck Study Number: 3475-244

Immunotherapeutic agents such as pembrolizumab (MK-3475) may produce antitumor effects by potentiating endogenous cancer-specific immune responses. The response patterns seen with such an approach may extend beyond the typical time course of responses seen with cytotoxic agents, and can manifest a clinical response after an initial increase in tumor burden or even the appearance of new lesions. Standard RECIST may not provide an accurate response assessment of immunotherapeutic agents such as pembrolizumab (MK-3475).

Therefore, RECIST 1.1 will be used with the following adaptations: If radiologic imaging shows initial PD, tumor assessment should be repeated ≥ 4 weeks later in order to confirm PD with the option of continuing treatment per below while awaiting radiologic confirmation of progression. If repeat imaging shows a reduction in the tumor burden compared to the initial scan demonstrating PD, treatment may be continued / resumed. If repeat imaging confirms progressive disease, subjects will be discontinued from study therapy. In determining whether or not the tumor burden has increased or decreased, investigators should consider all target lesions as well as non-target lesions. In subjects who have initial evidence of radiological PD, it is at the discretion of the treating physician whether to continue a subject on study treatment until repeat imaging is obtained a minimum of 4 weeks later. This clinical judgment decision should be based on the subject's overall clinical condition, including performance status, clinical symptoms, and laboratory data. Subjects may receive pembrolizumab (MK-3475) treatment while waiting for confirmation of PD if they are clinically stable as defined by the following criteria:

- Absence of signs and symptoms indicating disease progression
- No decline in ECOG performance status
- Absence of rapid progression of disease
- Absence of progressive tumor at critical anatomical sites (e.g., cord compression) requiring urgent alternative medical intervention.

When feasible, subjects should not be discontinued until progression is confirmed. This allowance to continue treatment despite initial radiologic progression takes into account the observation that some subjects can have a transient tumor flare in the first few months after the start of immunotherapy, but with subsequent disease response. Subjects that are deemed clinically unstable are not required to have repeat imaging for confirmation of progressive disease.

Measurable Disease

Measurable disease per RECIST 1.1 is defined as the presence of at least one measurable lesion. Measurable lesions are defined as those that can be accurately measured in at least one dimension (longest diameter to be recorded) as ≥ 20 mm by chest x-ray, as ≥ 10 mm with CT scan, or ≥ 10 mm with calipers by clinical exam. For irRC, measurable lesions are defined as those that can be accurately measured in at least two dimensions as 10x10mm with CT scan. All tumor measurements must be recorded in millimeters (or decimal fractions of centimeters).

Malignant Lymph Nodes

To be considered pathologically enlarged and measurable, a lymph node must be ≥ 15 mm in short axis when assessed by CT scan (CT scan slice thickness recommended to be no greater than 5 mm). At baseline and in follow-up, only the short axis will be measured and followed.

NU Study Number: NU 16G03
Merck Study Number: 3475-244

Non-measurable Lesions

For both RECIST 1.1 and irRC, all other lesions (or sites of disease), including small lesions (longest diameter <10 mm or pathological lymph nodes with ≥ 10 to <15 mm short axis), are considered non-measurable disease. Bone lesions, leptomeningeal disease, ascites, pleural/pericardial effusions, lymphangitis cutis/pulmonitis, inflammatory breast disease, and abdominal masses (not followed by CT or MRI), are considered as non-measurable.

Note: *Cystic lesions that meet the criteria for radiographically defined simple cysts should not be considered as malignant lesions (neither measurable nor non-measurable) since they are, by definition, simple cysts. 'Cystic lesions' thought to represent cystic metastases can be considered as measurable lesions, if they meet the definition of measurability described above. However, if non-cystic lesions are present in the same subject, these are preferred for selection as target lesions.*

6.2 Primary Endpoint

Measure **Objective Response Rate (ORR)** to guadecitabine and pembrolizumab in patients with recurrent platinum resistant Ovarian Cancer. Any patient who has completed at **least 2 cycles** of treatment will be evaluable for this endpoint.

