2.0 OBJECTIVES & ENDPOINTS

2.1 Primary Objective & Endpoint

Measure objective response rate (ORR) to guadecitabine and pembrolizumab in subjects with recurrent platinum resistant Ovarian Cancer (OC) using RECIST v1.1. The objective response rate as defined by RECIST v1.1 is the proportion of all subjects with confirmed PR or CR according to RECIST v1.1, from the start of treatment until disease progression/recurrence (taking as reference for progressive disease the smallest measurements recorded since the start of treatment).

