There is presumptive scientific rationale that treatment with a hypomethylating agent will cause re-expression of tumor antigens within the first 2 cycles, and thus epigenetic priming, which enhances the effects of immunotherapy. Therefore, it is reasonable to continue treatment with single agent pembrolizumab after epigenetic priming has been induced. If a patient cannot complete at least 2 cycles of guadecitabine and pembrolizumab combination, then she would be discontinued from the study.

Please note: Guadecitabine priming can be discontinued and the patient can continue on pembrolizumab monotherapy after 6 months (8 cycles), at the discretion of the treating physician, if the patient has stable disease or response. For patients who discontinued guadecitabine for reasons other than toxicity (i.e. disease stability of response > 6 months) and progress on pembrolizumab alone, a re-trial of guadecitabine in combination with pembrolizumab is possible, at the discretion of the treating physician, if the patient is clinically stable.

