4.9 Duration of Follow Up

Patients will have the ***first safety follow-up visit*** 30 days (\pm 7 days) after the last dose of study therapy or before the initiation of a new anti-cancer treatment, whichever is first.

All AEs that occur prior to the Safety Follow-Up Visit (30 days (\pm 7 days) after the last dose of study therapy) will be recorded. Subjects with an AE \geq Grade 2 that occurs \geq 30 days after discontinuation of study therapy and that is attributed (possibly, probably, or definitely) to the agent(s) will be followed until the AE is \leq Grade 1 or baseline, deemed clinically insignificant, and/or until a new anti-cancer treatment starts, whichever is earlier.

SAEs that occur within 90 days of the end of treatment or before initiation of a new anti-cancer treatment should also be followed and recorded per the guidelines stated above.

Subjects who discontinue trial treatment for a reason other than disease progression will move into the ***Long-term follow-Up Phase*** and will be assessed every 9 weeks (\pm 7 days) by radiologic imaging to monitor disease status until the start of new anti-neoplastic therapy, disease progression, death or end of the study. Information regarding post-study anti- neoplastic treatment will be collected if new treatment is initiated.

Once a subject experiences confirmed disease progression or starts a new anti-cancer therapy, the subject will move into the ***Survival follow-up phase*** and should be contacted by telephone or email or during clinic visits, every 3 months for the first 2 years after completing study therapy and then every 6 months thereafter to assess for survival status until death, withdrawal of consent, or the end of the study, whichever occurs first.

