10.2 Sample Size and Accrual

We will utilize the optimum two-stage design and we anticipate enrolling 35 evaluable patients. This two-stage design to test the null hypothesis that $RR \leq 0.10$ versus the alternative that $RR \geq 0.30$ (where RR is calculated via RECIST v1.1) has an expected sample size of 22.5 and a probability of early termination of 0.71 when $RR = 0.10$. If the drug combination is actually not effective, there is a 0.047 probability of concluding that it is (the target for this value was 0.050). If the drug is actually effective, there is a 0.098 probability of concluding that it is not (the target for this value was 0.100). Subjects who are not evaluable for response will be replaced so up to 46 subjects may be enrolled.

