10.3 Data Analysis Plans

10.3.1 Analysis Plans for Primary Objective

The primary outcome is objective response by RECIST v1.1. The proportion of patients having an objective response by RECIST 1.1 will be estimated with a 95% exact binomial confidence interval for the efficacy population. These confidence intervals will be adjusted for the sequential nature of the two-stage procedure ²⁴.

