10.4 Interim Analysis/Criteria for Stopping Study

10.4.1 Safety Criteria

The first 6 patients will be part of an initial safety run-in. A safety analysis will be done after all six patients have been observed for at least 2 weeks after completion of cycle 1. All toxicities will be tabulated. The study will move forward if ≤ 1 of 6 in the safety lead in cohort 1 experience a DLT (as defined in Section 4.3 and Table 3). If ≥ 2 of 6 in cohort 1 experience a DLT, the study will be suspended and an amendment to explore alternate dosing schemes will be considered. Toxicity counts and rates and the results of the analysis will be reviewed by the DMC. The patients enrolled in the safety lead in cohort will be included in the efficacy analysis.

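### The primary ORR leaves out treated patients who stop before completing 2 cycles (6.2, 10.2), although 2.1 counts all subjects and the efficacy population in 10.3.1 is never defined

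*Combined protocol and SAP*

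**What the plan says.** - Section 2.1 defines the primary endpoint as "the proportion of all subjects with confirmed PR or CR according to RECIST v1.1", counted from the start of treatment.
- Section 6.2 adds the evaluability condition: "Any patient who has completed at least 2 cycles of treatment will be evaluable for this endpoint".
- Section 10.2, like the study summary, provides for replacement: "Subjects who are not evaluable for response will be replaced so up to 46 subjects may be enrolled". The target is 35 evaluable patients.
- In Section 10.3.1 the proportion with an objective response "will be estimated with a 95% exact binomial confidence interval for the efficacy population", with the interval adjusted for the two-stage procedure. No section defines that population.
- Section 4.4.1 states: "If a patient cannot complete at least 2 cycles of guadecitabine and pembrolizumab combination, then she would be discontinued from the study".
- Section 5.1, footnote 4, sets the scan times on treatment: "radiologic imaging should be done prior to Cycle 3 and cycle 5 and then prior to every third cycle thereafter".
- Sections 4.4 and 6.3 already use a wider set, patients with at least one dose, for toxicity.
- The Amendment 9 rationale in Appendix V reports 5 patients who were enrolled but never started treatment, and 7 who had one cycle and were therefore held not evaluable for the primary endpoint. It gives no reasons for the 7.

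**The concern.** Whether a treated patient counts in the primary ORR depends partly on how she fares in her first 6 weeks (2 cycles of 21 days). A patient who dies, deteriorates clinically or stops for toxicity before completing cycle 2 is not a non-responder under 6.2. She is removed, and 10.2 puts another patient in her place. For toxicity the removal follows directly from 4.4.1. The first scheduled scan on treatment comes just before cycle 3, so most early leavers have no scheduled response assessment, and no rule counts them as failures.

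Section 6.2 does not contain the word only. The Amendment 9 rationale shows that the rule is applied as an exclusion. It is cited here as a record of use, not as a conflict with superseded text.

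At stake is the meaning of the primary estimate. A reader of 2.1 would take the ORR to describe patients who start the combination. Under 6.2 it describes those who stayed on it for 2 cycles.

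**Working it through.** **1. Reproducing the design.** Inputs from 10.2 and 10.4.2: 18 patients in stage 1, continue with 3 or more responders; 35 in total, positive with 7 or more; rates 0.10 and 0.30. The probability of a positive result at response rate p is

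P(p) = sum over x = 3 to 18 of Pr[Bin(18, p) = x] × Pr[Bin(17, p) ≥ max(0, 7 − x)].

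- P(0.10) = 0.0474; the plan states 0.047.
- 1 − P(0.30) = 1 − 0.9016 = 0.0984; the plan states 0.098.
- Expected sample size at 0.10: 18 + (1 − 0.7338) × 17 = 22.5; the plan states 22.5.

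These three figures reproduce with a binding stage-1 stop based on response. Section 10.4.2 makes the stop a matter for consideration and bases it on clinical benefit. With no stage-1 stop the first figure would be 0.055 before any exclusion. That is a separate matter, and the binding rule is used below.

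**2. Effect on the estimate.** Let q be the share of treated patients excluded and p_ex their response rate. Then

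ORR(treated) = (1 − q) × ORR(evaluable) + q × p_ex,

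so the overstatement is q × (ORR(evaluable) − p_ex).

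Take the smallest positive result, 7 responders in 35, with 6 treated patients set aside. The 6 is illustrative. It is the room under the cap of 46 if the 5 never-treated patients count toward it (46 − 5 − 35 = 6), which the documents do not settle. Intervals are exact 95% intervals, not adjusted for the two stages.

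- Evaluable set: 7/35 = 20.0% (8.4 to 36.9).
- All treated, none of the 6 responding: 7/41 = 17.1% (7.2 to 32.1). Check: 6/41 × 20.0 = 2.9 points.
- All treated, one of the 6 responding: 8/41 = 19.5%, so the gap nearly closes.

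**3. Effect on the type I error, only if the 0.10 null refers to all treated patients.** Setting ORR(treated) = 0.10 gives p_eval = (0.10 − q × p_ex)/(1 − q), and the type I error is P(p_eval). The documents give no planned share excluded, so q from 5% to 15% is an assumption.

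| Share excluded q | p_eval if p_ex = 0 | Type I error | p_eval if p_ex = 0.05 | Type I error |
|---|---|---|---|---|
| 5% | 0.1053 | 0.060 | 0.1026 | 0.053 |
| 10% | 0.1111 | 0.075 | 0.1056 | 0.060 |
| 15% | 0.1176 | 0.095 | 0.1088 | 0.069 |

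If p_ex = 0.10, p_eval is 0.10 and the figure stays 0.047. It also stays 0.047 if the null refers to evaluable patients.

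**The case against.** The strongest reply is that this is an evaluable-patient design and says so. The study summary, Section 3.0 and 10.2 speak of 35 evaluable patients, and 10.4.2 times the interim look by evaluable patients. On that reading the tested rate is the evaluable-patient ORR and 0.047 is correct. This stands. A reader might infer from the table above that the trial's type I error exceeds 5%. The documents do not support that: it needs an all-treated null, which the design text points away from, and an assumed response rate in the excluded below 0.10.

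Early leavers are also not certain non-responders. Section 4.9 keeps imaging some of them: "Subjects who discontinue trial treatment for a reason other than disease progression will move into the" long-term follow-up phase. Section 4.4.1, however, speaks of leaving the study, so it is unclear whether the patients it covers are imaged. Loss through progression may be small. Progression first seen at the scan before cycle 3 normally comes after 2 completed cycles and stays in, and 4.10 and 6.1 favour continuing until progression is confirmed. The reasons for the 7 exclusions are unknown, so they cannot be read as treatment failures.

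Two further conflicts might be inferred, and both are weak. Section 10.4.1 says "The patients enrolled in the safety lead in cohort will be included in the efficacy analysis"; the natural meaning is that the run-in cohort is pooled with the rest, not that evaluability is waived for it. Section 4.11 allows replacement of patients never dosed but does not say that only they may be replaced.

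The reply does not remove the mismatch between 2.1 and 6.2, the undefined population in 10.3.1, or the effect on the estimate.

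**Conclusion.** The point holds as one about the primary estimate and its population. Followed as written, the plan drops treated early leavers from the ORR. The reported rate then exceeds the rate among patients who start treatment whenever the excluded respond less often than those retained. That direction is likely but not certain. At the margin of a positive result the gap is about 3 percentage points (20.0% against 17.1%), assuming 6 excluded and no responders among them.

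The type I error is a conditional matter. It is 0.047 on the reading that the design text favours. It is 0.060, 0.075 or 0.095 at an assumed 5%, 10% or 15% excluded only if the null covers all treated patients and none of the excluded would respond, and 0.053, 0.060 or 0.069 if 5% of them would. The documents never state which population the 0.10 and 0.30 rates describe. This should be fixed, but it does not invalidate the two-stage decision.

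**What to change.** 1. Define the efficacy population in 10.3.1 and reconcile 2.1 with 6.2 and 10.2.
2. Keep the 2/18 and 6/35 decision, and its two-stage-adjusted interval, on the evaluable set as run. Moving the decision to treated patients now would change the rule in an open-label trial after patients have been set aside. Making the all-treated ORR primary while the decision stays on evaluable patients would put the two on different populations.
3. Beside that result, always report the ORR among all patients who received at least one dose. Count those with no post-baseline response assessment as non-responders, and label the exact interval as not adjusted for the two-stage design.
4. List the reason each treated patient was set aside, including the 7 in Amendment 9.
5. State whether the 0.10 and 0.30 rates describe treated or evaluable patients.
6. Date the change and mark it as late.

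The cost is wording in a few sections and one extra estimate, with no extra patients or assessments. The downside for the sponsor is that a somewhat lower ORR may stand beside the main figure.
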